6.3.2. Additional considerations

NA

6.4. Analysis of safety

6.4.1. Analysis of safety & reactogenicity planned in the protocol

The primary analyses of safety and reactogenicity will be based on the TVC.

- The percentage of subjects with at least one local AE (solicited and unsolicited), with at least one general AE (solicited and unsolicited) and with any AE during the 4-day (Day 0 to Day 3) follow-up period after the vaccination will be tabulated with exact 95% CI [Clopper, 1934]. The same calculations will be performed for any Grade 3 (solicited or unsolicited) symptoms, relationship to the vaccination and any symptoms requiring medical attention.
- The percentage of subjects reporting each individual solicited symptom during the 4-day follow-up period with exact 95% CI [Clopper, 1934], by type of adverse event; by severity (any grade, Grade 3 only); by relationship to vaccination (any relationship, related only) and any symptoms requiring medical attention will be tabulated.
- The occurrence of fever will be tabulated per 0.5°C cumulative increments as well as the occurrence of Grade 3 fever ($> 39.0^{\circ}\text{C}$ axillary temperature) with causal relationship to vaccination.
- The percentage of subjects with at least one report of unsolicited adverse event classified by the Medical Dictionary for Regulatory Activities and reported within the 31-day (Day 0 to Day 30) follow-up period after vaccination will be tabulated with exact 95% CI [Clopper, 1934]. The same tabulation will be performed for Grade 3 unsolicited adverse events, for unsolicited adverse events with a causal relationship to vaccination, and for unsolicited adverse events requiring medical attention.
- The percentage of subjects who started receiving at least one concomitant medication (i.e. any medication, antipyretic medication, prophylactic antipyretics) during the 4-day and 31-day follow-up period after vaccination will be tabulated (with exact 95% CI) [Clopper, 1934].
- SAEs and withdrawals due to AEs and SAEs reported during the study will be described in detail

6.4.2. Additional considerations

6.4.2.1. Combined Solicited and Unsolicited Adverse Events

For clinicaltrials.gov and EudraCT posting purposes, a summary of combined solicited and unsolicited non-serious adverse events will be produced by System Organ Class and preferred terms and according to occurrence of each event.

A summary of subjects with all combined solicited (regardless of their duration) and unsolicited adverse events will be provided. Solicited adverse events will be coded by MedDRA as per the following codes.

Solicited symptom	Lower level term code	Corresponding Lower level term decode
PA	10022086	Injection site pain
RE	10022098	Redness at injection site
SW	10053425	Swelling at injection site
FA	10016256	Fatigue
TE	10016558	Fever
GI	10017944	Gastrointestinal disorder
HE	10019211	Headache

7. ANALYSIS INTERPRETATION

All analyses are descriptive.

8. CONDUCT OF ANALYSES

8.1. Sequence of analyses

The analyses will be performed when all data up to one month after the vaccine dose will be available. All analyses and associated individual data will be presented in a Clinical Study Report, which will be shared with the investigator(s) involved in the conduct of this study.

Description	Analysis ID	Disclosure Purpose (CTRS=public posting, SR=study report, internal, public posting)	Dry run review needed (Y/N)	Study Headline Summary (SHS)requiring expedited communication to upper management (Yes/No)	Reference for TFL
Analysis of epoch 1	E1_01	SR	Yes	Yes	TFL TOC Statistical peer review version - All TFLs

8.2. Statistical considerations for interim analyses

All analyses will be conducted on final data and therefore no statistical adjustment for interim analyses is required.

9. CHANGES FROM PLANNED ANALYSES

The major changes from the protocol are,

- According-to-protocol cohort for analyses of antibody persistence defined in the protocol for the analysis of antibody persistence was removed from the SAP to reduce the number of cohorts used in the analysis. The analysis of persistence and response to challenge dose will be performed on the According-to-protocol cohort for analyses of immunogenicity. This change will not have significant impact on the analysis of persistence as no major difference in number of subjects expected between the ATP cohort for analysis of Immunogenicity and ATP cohort for analyses of antibody persistence.

Other changes include,

- The analysis for persistence and response to challenge dose is harmonized with respect to the cut-offs to consider.
 - The analysis to summarize the number and percentage of subjects between >10 mIU/mL and < 100 mIU/mL planned in the protocol was removed to be consistent with the endpoints of the study.
 - The analysis to summarize the post challenge dose response and anamnestic response stratified by the pre-challenge dose concentrations will be performed by considering the categories < 6.2 mIU/ml, ≥ 6.2 mIU/ml - < 10 mIU/ml, and ≥ 10 mIU/ml at pre-challenge dose time point.
- All the analysis of solicited and/or unsolicited adverse events will be performed for any, grade 3, by relationship to vaccination, and requiring medical attention to be consistent with the presentation of the adverse events summary.

10. LIST OF FINAL REPORT TABLES, LISTINGS AND FIGURES

The TFL TOC provides the list of tables/listings and figures needed for the study report. It also identifies the tables eligible for each analyses and their role (synopsis, in-text, post-text, SHS, CTRS,...). Note that all TFL aimed to be included as post-text are noted as post-text even if these are tabulation of individual data such as listing of SAE. The post-text material contains all source material for the study report and accordingly a post-text table may be redundant with an in-text table.

The following group name will be used in the TFLs, to be in line with the treatment dataset:

Group order in tables	Group label in tables	Group definition for footnote	Pooled Groups label in tables	Pooled definition for footnote
1	HBV Group	Subjects who previously received 4 doses of Infanrix hexa in first two years of life and received a challenge dose of HBV vaccine in this study	HBV Group	HBV Group

11. ANNEX 1 STANDARD DATA DERIVATION RULE AND STATISTICAL METHODS

11.1. Statistical Method References

The exact two-sided 95% CIs for a proportion within a group will be the Clopper-Pearson exact CI [Clopper CJ, Pearson ES. The use of confidence or fiducial limits illustrated in the case of binomial. *Biometrika*. 1934;26:404-413].

11.2. Standard data derivation

11.2.1. Date derivation

- SAS date derived from a character date: in case day is missing, 15 is used. In case day & month are missing, 30June is used.
- Onset day for an event (AE, medication, vaccination...): the onset day is the number of days between the last study vaccination & the onset/start date of the event. This is 0 for an event starting on the same day as a vaccination. See SAS date derived in case the start date of the event is incomplete.

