8.3. Detecting and recording adverse events, serious adverse events and pregnancies

8.3.1. Time period for detecting and recording adverse events, serious adverse events and pregnancies

All AEs starting 30 days following administration of the dose of study vaccine (Day 0 to Day 30) must be recorded into the appropriate section of the eCRF, irrespective of intensity or whether or not they are considered vaccination-related.

The time period for collecting and recording SAEs will begin at the receipt of study vaccine and will end 30 days following administration of the dose of study vaccine for each subject. See Section [8.4](#) for instructions on reporting of SAEs.

All AEs/SAEs leading to withdrawal from the study will be collected and recorded from the time of the receipt of study vaccine.

In addition to the above-mentioned reporting requirements and in order to fulfil international reporting obligations, SAEs that are related to study participation (i.e. protocol-mandated procedures, invasive tests, a change from existing therapy) or are related to a concurrent GSK medication/vaccine will be collected and recorded from the time the subject consents to participate in the study until she/he is discharged from the study.

The time period for collecting and recording pregnancies will begin at the receipt of study vaccine and will end 30 days following administration of the dose of study vaccine. See section [8.4](#) for instructions on reporting of pregnancies.

An overview of the protocol-required reporting periods for AEs, SAEs, and pregnancies is given in [Table 13](#).

Table 13 Reporting periods for collecting safety information

Event	Pre HBV challenge(Consent obtained)	HBV challenge (Visit 1)	4-day post HBV challenge follow-up	31-day post HBV challenge follow-up (Visit 2) Study conclusion
Time in study		Day 0	Day 3	Day 30
Solicited local and general AEs				
Unsolicited AEs				
AEs/SAEs leading to withdrawal from the study				
SAEs				
SAEs related to study participation or concurrent GSK medication/vaccine				
Pregnancies				

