11.2.2. Dose number

- The study dose number is defined in reference to the number of study visits at which vaccination occurred. Specifically in this study, dose 1 refers to all vaccines administered at the first vaccination visit.
- Relative dose: the relative dose for an event (AE, medication, vaccination) is the most recent study dose given before an event. In case the event takes place on the day a study dose is given, the related dose will be that of the study dose, even if the event actually took place before vaccination. For instance, if an adverse event begins on the day of the study vaccination but prior to administration of the vaccine, it will be assigned to this dose.

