11.2.5. Safety/Reactogenicity

- For the analyses of solicited symptoms, missing or non-evaluable measurements will not be replaced. Therefore the analyses of the solicited symptoms based on the TVC will include only subjects with documented safety data (i.e. symptom screen completed).
- For the analyses of unsolicited adverse events/concomitant medication, all vaccinated subjects will be considered and subjects who did not report an event will be considered as subjects without an event.
- The maximum intensity of local injection site redness/swelling will be scored at GSK Biologicals as follows:

0	:	Absent
1	:	≤ 20 mm
2	:	>20 and ≤ 50 mm
3	:	> 50 mm

- The maximum intensity of fever will be scored at GSK Biologicals as follows:

Axillary	
0	: $< 37.5^{\circ}\text{C}$
1	: $\geq 37.5^{\circ}\text{C}$ and $\leq 38.0^{\circ}\text{C}$
2	: $> 38.0^{\circ}\text{C}$ and $\leq 39.0^{\circ}\text{C}$
3	: $> 39.0^{\circ}\text{C}$

Note that for all tables described in this section, the way the percentage of subjects will be derived will depend on the event analysed (see table below for details). As a result, the N value may differ from one table to another.

Event	N used for deriving % per subject for Vaccination phase
Solicited general symptom	All subjects with at least one solicited general symptom documented as either present or absent (i.e., symptom screen completed)
Solicited local symptom	All subjects with at least one solicited local symptom documented as either present or absent (i.e., symptom screen completed)
Unsolicited symptom	All subjects with study vaccine administered
Concomitant medication	All subjects with study vaccine administered

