White - Caucasian / European Heritage, n (%)	
White - Arabic / North African Heritage, n (%)	

HBV Group= Subjects who previously received 4 doses of Infanrix hexa in first two years of life and received a challenge dose of HBV vaccine in this study

SD - Standard Deviation

N - Total number of subjects enrolled in the study

n (%) - Number (percentage) of subjects in a given category

Template 26 Solicited and Unsolicited symptoms experienced by at least 5 % of subjects classified by MedDRA Primary System Organ Class and Preferred Term within the 31-day (Days 0-30) post-vaccination - SAE excluded (Total Vaccinated cohort)

			HBV Group N = XXX		95% CI	
Primary System Organ Class (CODE)	Preferred Term (CODE)	n*	n	%	LL	UL
At least one symptom						
Blood and lymphatic system disorders (10005329)	Leukocytosis (10024378)					
Cardiac disorders (10007541)	Angina unstable (10002388)					
	Mitral valve disease (10061532)					
	Myocardial infarction (10028596)					
Respiratory, thoracic and mediastinal disorders (10038738)	Pleural effusion (10035598)					
	Pneumothorax (10035759)					

HBV Group= Subjects who previously received 4 doses of Infanrix hexa in first two years of life and received a challenge dose of HBV vaccine in this study

At least one symptom = at least one symptom experienced (regardless of the MedDRA Preferred Term)

N = number of subjects with the administered dose

n* = number of events reported

n/%,= number/percentage of subjects reporting the symptom at least once

95% CI = exact 95% confidence interval; LL = Lower Limit, UL = Upper Limit

Template 27 Number of subjects by country

	HBV Group N = xxx
Country	N
Xxxxx	
Xxxxx	
Xxx	

HBV Group= Subjects who previously received 4 doses of Infanrix hexa in first two years of life and received a challenge dose of HBV vaccine in this study

N = number of subjects

n= number of enrolled subjects included in each group

Template 28 Number of enrolled subjects by age category

Characteristics	Categories	HBV Group N =
Age category	n	
In utero		
Preterm newborn infants (gestational age < 37 wks)		
Newborns (0-27 days)		
Infants and toddlers (28 days-23 months)		
Children (2-11 years)		
Adolescents (12-17 years)		
Adults (18-64 years)		
From 65-84 years		
85 years and over		
Missing		

HBV Group= Subjects who previously received 4 doses of Infanrix hexa in first two years of life and received a challenge dose of HBV vaccine in this study

N = Number of enrolled subjects

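### SAP 11.2.1 imputes partial onset dates without a bound at vaccination or Day 30, so a few unsolicited AEs could leave the 31-day tables if onset day selects the rows (minor)

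*SAP*

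**What the plan says.** SAP 11.2.1 gives one rule for incomplete dates: "in case day is missing, 15 is used. In case day & month are missing, 30June is used". The same section defines onset day as the interval from the last study vaccination to the start of the event, and links the two: "See SAS date derived in case the start date of the event is incomplete". No limit is placed on the result.

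SAP 11.2.2 assigns each event to "the most recent study dose given before an event", with an exception only for events on the day of vaccination. SAP 6.4.1 plans the percentage of subjects with an unsolicited AE "reported within the 31-day (Day 0 to Day 30) follow-up period after vaccination will be tabulated with exact 95% CI". The denominator is fixed in SAP 11.2.5: "all vaccinated subjects will be considered and subjects who did not report an event will be considered as subjects without an event". SAP 11.2.6 covers missing reports and does not mention partial dates.

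On collection, Protocol 8.3.1 states: "All AEs starting 30 days following administration of the dose of study vaccine (Day 0 to Day 30) must be recorded".

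**The concern.** The rule can place an event outside the period for which it was collected, even when the recorded month is compatible with that period. An AE dated only March 2016 after a dose on 20 March is set to 15 March, onset day -5. An AE dated only April 2016 after a dose on 10 March is set to 15 April, onset day 36. Under Protocol 8.3.1 both were presumably in-window events, on Day 0 to 11 and Day 22 to 30 respectively.

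If the tables keep only onset days 0 to 30, both events disappear from them. The relative-dose rule does not bring back the first, because no dose precedes the imputed date. A subject with no other event is then counted as event-free in an unchanged denominator. Displacing a true in-window event can therefore only lower a safety percentage.

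**Working it through.** The documents give no figure on this point, so there is none to reproduce. The check enumerates dates.

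**Inputs from the documents.** The imputation and onset-day rules (SAP 11.2.1); the Day 0 to 30 window (SAP 6.4.1, Protocol 8.3.1); about 300 subjects and about six months of enrolment (Protocol 4.1); a 21 to 48 day interval to Visit 2 (Protocol 5.5, Table 5).

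**Assumptions.** Dose dates uniform over the 366 days of 2016; true onset uniform over Day 0 to 30; day missing, month and year known.

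**Step 1: day missing.** Onset day = (15th of the onset month) - (dose date). There are 366 x 31 = 11,346 cases.

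- Below 0: 1,537 / 11,346 = 13.55%.
- Above 30: 1,260 / 11,346 = 11.11%.
- Outside the window: 2,797 / 11,346 = 24.65%.

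Over the twelve possible six-month enrolment periods the total is 24.4% to 24.8%. With true onset on Day 0 to 14 it is 27.9%, and on Day 0 to 3 it is 45.9%, all before the dose. Uniform onset is therefore the milder assumption.

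**Step 2: day and month missing.** 30 June lies within Day 0 to 30 for only 31 of 366 dose dates (8.5%). By six-month enrolment period the share is 0% to 17.0%. Such dates should be very rare.

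**Step 3: size in the table.** The rate of missing days is not in the documents, so 1% to 10% is assumed. Also assumed: 60 of 300 subjects with one unsolicited AE each. Subjects lost = 60 x rate x 0.2465.

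| Missing-day rate | Subjects lost | Points of 300 |
|---|---|---|
| 1% | 0.15 | 0.05 |
| 5% | 0.74 | 0.25 |
| 10% | 1.48 | 0.49 |

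Losing one subject moves 60/300 = 20.0% (exact 95% CI 15.6% to 25.0%) to 59/300 = 19.7% (15.3% to 24.6%).

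**Step 4: does a bound help?** Moving the imputed date to the nearest day that lies both in the recorded month and in Day 0 to 30 leaves 0 of the 11,346 cases outside. It can also admit events that truly lie outside. Let r be the share of such entries, and s and b the proportions of them counted in the window under the SAP rule and under the bound. Errors are (1 - r) x 0.2465 + r x s for the SAP rule and r x b for the bound. They are equal at r = 0.2465 / (0.2465 + b - s).

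| True onset | s | b | Break-even r |
|---|---|---|---|
| Day 31 to 48 | 23.3% | 68.9% | 35.1% |
| Day -30 to -1 | 11.5% | 49.2% | 39.5% |
| Day -14 to -1 | 24.6% | 75.4% | 32.7% |

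With r = 10% on Day 31 to 48, errors are 6.9% with the bound against 24.5% now.

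**Step 5: where the bound does not help.** For Day 0 to 3 membership, under uniform onset, the bound misclassifies 18.8% against 17.1% now. For medications truly started earlier in the dose month with the day missing (5,401 cases), the bound would count 100% as starts in the window, against 23.3% now.

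**The case against.** The strongest objection is that the SAP never says onset day selects the rows. SAP 6.4.1 speaks of events reported within Day 0 to 30, and AEs enter the eCRF because they belong to that period. If selection follows the recording period, nothing is lost. This stands as a condition on the whole point. But onset day is the only derived quantity that places an event in time relative to the dose, so it is the natural selector. If another rule is used, the SAP should state it.

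Second, partial dates should be rare. Diary cards are verified at Visit 2 (Protocol 5.6.12), omissions may be queried (Protocol 11.1), and all analyses are descriptive (SAP 7). This stands, and it sets the priority.

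Third, the presumption that a displaced event is in-window is not certain. Protocol 8.1.1 also counts newly detected conditions that may predate the study, and Visit 2 may fall as late as Day 48. This stands too, and is why the break-even shares are shown.

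Two stronger readings are tempting. A reader might infer that terms would vanish from Template 26 ("Solicited and Unsolicited symptoms experienced by at least 5 % of subjects classified by MedDRA"), which serves registry posting. That needs a term at exactly 15 of 300 subjects, and the documents give no reason to expect one. A reader might also infer that medication starts need the same bound, since onset day covers them. The documents do not support that. Protocol 6.7.1 records drugs given during Day 0 to 30 whenever they were started, while SAP 6.4.1 counts those newly started, so a bound would turn ongoing drugs into new starts.

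**Conclusion.** The point holds as a minor one. The missing bound is a fact of SAP 11.2.1; the loss of events depends on onset day selecting the rows. On that reading about 25% of in-window unsolicited AEs with a missing day leave the 31-day tables, or 28% if onset is on Day 0 to 14. In a mid case this is about one subject or fewer in 300, with the AE frequency and the partial-date rate both assumed. The direction for true in-window events is towards understatement. The documents do not establish that any AE will be dropped. The primary endpoint, the other immunogenicity analyses and the whole-study SAE table are untouched.

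**What to change.** For unsolicited AEs in the 31-day tables only:

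- State that onset day selects the rows, or state the rule that does.
- Keep the 15th. If that date falls before vaccination or after Day 30 and the recorded month overlaps Day 0 to 30, use the nearest date in that month between vaccination and Day 30. Make an exception when a recorded date part or end date shows onset outside the window.
- If day and month are both missing and the recorded year is compatible, count the AE in the 31-day window without assigning an onset day.
- List all AEs with imputed dates.

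Do not apply the bounded date to medication start dates or to the 4-day table.

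The cost is a short addition to SAP 11.2.1, some programming and one listing. The downside is that a few events truly before the dose or after Day 30 may be counted in the window. The bound still gives fewer errors than the current rule unless roughly a third or more of day-missing entries truly lie outside.

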11.2.2. Dose number

- The study dose number is defined in reference to the number of study visits at which vaccination occurred. Specifically in this study, dose 1 refers to all vaccines administered at the first vaccination visit.
- Relative dose: the relative dose for an event (AE, medication, vaccination) is the most recent study dose given before an event. In case the event takes place on the day a study dose is given, the related dose will be that of the study dose, even if the event actually took place before vaccination. For instance, if an adverse event begins on the day of the study vaccination but prior to administration of the vaccine, it will be assigned to this dose.

11.2.3. Demography

- Age: Age at the reference activity, computed as the number of units between the date of birth and the reference activity.

11.2.4. Immunogenicity

- A seronegative subject is a subject with anti-HBs antibody concentration below the assay cut-off (< 6.2 mIU/ml).
- A seropositive subject is a subject with anti-HBs antibody concentrations above the assay cut-off (≥ 6.2 mIU/ml).

- A seroprotected subject is a subject with anti-HBs antibody concentrations above the protection level (≥ 10 mIU/ml).
- Anamnestic response to the single challenge dose is defined as:
 - At least (i.e. greater than or equal to) 4-fold rise in post-vaccination anti-HBs antibody concentrations in subjects seropositive at the pre-vaccination time point.
 - Post-vaccination, anti-HBs antibody concentrations ≥ 10 mIU/ml in subjects seronegative at the pre-vaccination time point.
- The Geometric mean antibody concentrations (GMCs) calculations will be performed by taking the anti-log of the mean of the \log_{10} concentration transformations. All subjects will be considered. Subjects whose antibody concentrations are below the cut-off of the assay will be given an arbitrary value of half the cut-off for the purpose of GMC calculation. Note that as per assay specification, results between the assay cut-off of 6.2 mIU/ml and 7.65 mIU/ml (= Lower limit of Quantification) will be quantified as 6.2 mIU/ml.
- For a given subject and a given immunogenicity measurement, missing or non-evaluable measurements will not be replaced. Therefore, an analysis will exclude subjects with missing or non-evaluable measurements.
- All CI computed will be two-sided 95% CI.

